6.2.2.6 Management of stomatitis / oral mucositis / mouth ulcers

Adverse Drug Reaction	Severity	Afinitor Dose Adjustment and Management Recommendations
Stomatitis	Grade 1 (Minimal symptoms, normal diet)	No dose adjustment required. Manage with non-alcoholic or salt water (0.9%) mouth wash several times a day.
	Grade 2 (Symptomatic but can eat and swallow modified diet)	Temporary dose interruption until recovery to grade ≤ 1 . Re-initiate Afinitor at the same dose. If stomatitis recurs at grade 2, discontinue Afinitor. Manage with topical analgesic mouth treatments (e.g. benzocaine, butyl aminobenzoate, tetracaine hydrochloride, menthol or phenol) with or without topical corticosteroids (i.e. triamcinolone oral paste)*.
	Grade 3 (Symptomatic and unable to adequately eat or hydrate orally)	Discontinue Everolimus
	Grade 4 (Symptoms associated with life-threatening consequences)	Discontinue Afinitor and treat with appropriate medical therapy.

* using agents containing alcohol, hydrogen peroxide, iodine, and thyme derivatives in management of stomatitis as they may worsen mouth ulcers.

Patients with a clinical history of stomatitis/mucositis/mouth ulcers and those with gastrointestinal morbidity associated with mouth/dental infections, irritation of esophageal mucosa e.g. gastroesophageal reflux disease (GERD) and pre-existing stomatitis/mucositis must be monitored even more closely. Patients should be instructed to report the first onset of buccal mucosa irritation/reddening to their study physician immediately.

Stomatitis/oral mucositis/mouth ulcers due to Everolimus should be treated using local supportive care. Please note that investigators in earlier trials have described the oral toxicities associated with Everolimus as mouth ulcers, rather than mucositis or stomatitis. If your examination reveals mouth ulcers rather than a more general inflammation of the mouth, please classify the adverse event as such. The suggested paradigm for treatment of stomatitis/oral mucositis/mouth ulcers is as follows:

1. For mild toxicity (grade 1), no dose adjustment required. Manage with non-alcoholic mouth wash or salt water (0.9%) mouth wash several times a day until resolution.
2. For more severe toxicity (grade 2 in which case patients have pain but are able to maintain adequate oral alimentation, or grade 3 in which case patients cannot maintain adequate oral alimentation), the suggested treatments are topical analgesic mouth treatments (i.e., local anesthetics such as, benzocaine, butyl aminobenzoate, tetracaine hydrochloride, menthol, or phenol) with or without topical corticosteroids, such as triamcinolone oral paste 0.1% (Kenalog in Orabase®).
3. Agents containing alcohol, hydrogen peroxide, iodine, and thyme derivatives may tend to worsen mouth ulcers. These agents should be avoided.
4. Antifungal agents should be avoided unless a fungal infection is diagnosed. In particular, systemic imidazole antifungal agents (ketoconazole, fluconazole, itraconazole, etc.) should be avoided in all patients due to their strong inhibition of Everolimus metabolism, therefore leading to higher Everolimus exposures. Therefore, topical antifungal agents are preferred if an infection is diagnosed.

6.2.2.7 Management of diarrhea

Appearance of grade 1-2 diarrhea attributed to study drug toxicity may be treated with supportive care such as loperamide, initiated at the earliest onset (for example 4 mg orally followed by 2 mg orally every 2 hours until resolution of diarrhea).

6.2.2.8 Management of hyperlipidemia and hyperglycemia

Adverse Drug Reaction	Severity	Afinitor Dose Adjustment and Management Recommendations
Metabolic events (e.g. hyperglycemia, dyslipidemia)	Grade 1	No dose adjustment required. Initiate appropriate medical therapy and monitor.
	Grade 2	No dose adjustment required. Manage with appropriate medical therapy and monitor.
	Grade 3	Discontinue Everolimus
	Grade 4	Discontinue Everolimus

Treatment of hyperlipidemia should take into account the pre-treatment status and dietary habits of the patient. Grade 2 or higher hypercholesterolemia (>300 mg/dL or 7.75 mmol/L) or grade 2 hypertriglyceridemia or higher (>2.5 x upper normal limit) should be treated with a 3-hydroxy-3-methyl-glutaryl (HMG)-CoA reductase inhibitor (e.g. atorvastatin, pravastatin, fluvastatin) or appropriate triglyceride-lowering medication, in addition to diet.

Note: Concomitant therapy with fibrates and an HMG-CoA reductase inhibitor is associated with an increased risk of a rare but serious skeletal muscle toxicity manifested by rhabdomyolysis, markedly elevated creatine phosphokinase (CPK) levels and myoglobinuria, acute renal failure and sometimes death. The risk versus benefit of using this therapy should be determined for individual patients based on their risk of cardiovascular complications of hyperlipidemia.

Dyslipidemia (including hypercholesterolemia and hypertriglyceridemia) has been reported in patients taking everolimus. Monitoring of blood cholesterol and triglycerides prior to the start of everolimus therapy and periodically thereafter as well as management with appropriate medical therapy is recommended.

Hyperglycemia has been reported in patients taking everolimus. Monitoring of fasting serum glucose is recommended prior to the start of Everolimus and periodically thereafter. More frequent monitoring is recommended when everolimus is co-administered with other drugs that

may induce hyperglycemia. Optimal glycemic control should be achieved before starting a patient on Everolimus.

6.2.2.9 Management of non-infectious pneumonitis

Non-infectious pneumonitis is a class effect of rapamycin derivatives. Cases of non-infectious pneumonitis (including interstitial lung disease) have also been described in patients taking Everolimus. Some of these have been severe and on rare occasions, a fatal outcome was observed.

- A diagnosis of non-infectious pneumonitis should be considered in patients presenting with non-specific respiratory signs and symptoms such as hypoxia, pleural effusion, cough or dyspnea, and in whom infectious, neoplastic and other non-medicinal causes have been excluded by means of appropriate investigations. Opportunistic infections such as PJP should be ruled out in the differential diagnosis of non-infectious pneumonitis. Patients should be advised to report promptly any new or worsening respiratory symptoms.

Patients who develop radiological changes suggestive of non-infectious pneumonitis and have few or no symptoms may continue Afinitor therapy without dose alteration.

If symptoms are moderate (grade 2), consideration should be given to interruption of therapy until symptoms improve. The use of corticosteroids may be indicated. Afinitor may be reintroduced at a daily dose approximately 50% lower than the dose previously administered.

For cases of grade 3 non-infectious pneumonitis, discontinue Afinitor. For cases of grade 4 non-infectious pneumonitis, Afinitor therapy should be discontinued. Corticosteroids may be indicated until clinical symptoms resolve.

For patients who require use of corticosteroids for treatment of non-infectious pneumonitis, prophylaxis for pneumocystis jirovecii pneumonia (PJP) may be considered. The two compounds studied most extensively for prophylaxis against PJP have been trimethoprim-sulfamethoxazole, given orally, and pentamidine, given as an aerosol.

If non-infectious pneumonitis develops, the guidelines in Table 6-3 should be followed. Consultation with a pulmonologist is recommended for any case of pneumonitis that develops during the study.

Table 6-3 Management of non-infectious pneumonitis

Worst grade pneumonitis	Suggested investigations	Management of pneumonitis	Everolimus dose adjustment
Grade 1 (Asymptomatic, radiographic findings only)	CT scans with lung windows.	No specific therapy is required	No dose adjustment required. Initiate appropriate monitoring.
Grade 2 (Symptomatic, not interfering with Activities of Daily Living)	CT scan with lung windows. Consider pulmonary function testing includes: spirometry, DLCO, and room air O ₂ saturation at rest. Consider a bronchoscopy with biopsy and/or BAL. Monitoring at each visit until return to ≤ grade 1. Return to initial monitoring frequency if no recurrence.	Symptomatic only. Consider corticosteroids and/or other supportive therapy if symptoms are troublesome.	Rule out infection and consider interruption of Everolimus until symptoms improve to Grade ≤ 1.
Grade 3 (Symptomatic, Interfering with Activities of Daily Living. O ₂ indicated)	CT scan with lung windows and pulmonary function testing includes: spirometry, DLCO, and room air O ₂ saturation at rest. Monitoring at each visit until return to ≤ grade 1. Return to initial monitoring frequency if no recurrence. Bronchoscopy with biopsy and/or BAL is recommended.	Consider corticosteroids if infective origin is ruled out. Taper as medically indicated.	Rule out infection and discontinue Everolimus until symptoms improve to Grade ≤ 1.
Grade 4 (Life-threatening, ventilator support indicated)	CT scan with lung windows and required pulmonary function testing, if possible, includes: spirometry, DLCO, and room air O ₂ saturation at rest. Monitoring at each visit until return to ≤ grade 1. Return to initial monitoring frequency if no recurrence. Bronchoscopy with biopsy and/or BAL is recommended if possible.	Consider corticosteroids if infective origin is ruled out. Taper as medically indicated.	Rule out infection and discontinue Everolimus.

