4.1 Description of study design

Patients treated with curative intent either in the post-operative or definitive setting with high dose radiotherapy (≥ 50 Gy) with or without chemotherapy will be eligible. There will be one treatment group with each patient serving as their own control. Patients would have their salivary output measured before radiotherapy, 3 weeks after the start of radiotherapy, and at the end of radiotherapy (6 weeks). Patients who demonstrate more than a 50% decrease in

saliva flow rates will enter the treatment phase of the trial. Based on expert experience, we estimate that half the treated patients will exhibit a decrease of 50% or more in flow rate. These affected patients will then receive the planned dose of everolimus **once a day for 5 days, starting two weeks after the completion of radiotherapy**. Salivary output measurements will be obtained prior to everolimus administration and at completion of the 5 day everolimus course and at 1 month, 3 months and 6 months after the completion of radiation or chemoradiation therapy.

It is our expectation that because of the short exposure to everolimus (a total of 5 days only), the well described everolimus related toxicities will not develop.

However, following discussions with the company (Novartis), two dose levels will be evaluated: a starting dose of 5 mg po daily, will initially be evaluated in a cohort of 3 patients.

For the purpose of this trial, dose-limiting toxicity (DLT) is defined as an everolimus-related grade 3 or higher AE.

Toxicity will be graded based on the Common Terminology Criteria for Adverse Events (CTCAE) Version4.03.

(<http://www.hrc.govt.nz/sites/default/files/CTCAE%20manual%20-%20DMCC.pdf>)

As mentioned, we will start treating enrolled patients on the lower dose level.

-If no DLT occurs, will proceed with dose escalation to the full FDA-approved dose (10 mg po daily) [in this case, total number of patients in the trial: 13; 3 in the 5 mg cohort, 10 in the 10 mg cohort].

-If 1 DLT occurs, cohort will be expanded to additional 3 patients; and if another DLT occurs in this expanded cohort, no escalation to full dose (10 mg po daily) will be attempted, and cohort will be expanded to 10 patients [in this case, total number of patients in the trial: 10; all in the 5 mg cohort];

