6.2.1.2 Dosing modifications

For patients who do not tolerate the protocol-specified dosing schedule, dose adjustments are not permitted.

Table 6-1 and Table 6-2 list the dosing guidelines for Everolimus-related non-hematologic and hematologic toxicities.

Management of severe or intolerable adverse drug reactions (ADRs) may require temporary dose interruption of Afinitor therapy.

The proceeding sections summarize recommendations for dose interruption, or discontinuation of Afinitor in the management of ADRs. General management recommendations are also provided as applicable. Clinical judgment of the treating physician should guide the management plan of each patient based on individual benefit/risk assessment.

Table 6-1 Dosing guidelines for Everolimus-related non-hematologic toxicities

Toxicity	Action
Non-Infectious Pneumonitis	Discontinue Everolimus.
Reactivation of HBV or HCV flare	Discontinue Everolimus.
AST or ALT elevation Grade 1 ($>$ ULN - 3.0 x ULN)	Maintain current dose level
Grade 2 ($>$ 3.0 - 5.0 x ULN)	
AST or ALT elevation Grade 3 ($>$ 5.0 - 20.0 ULN)*	Discontinue Everolimus
AST or ALT elevation Grade 4 ($>$ 20 x ULN)*	Discontinue Everolimus
Intolerable grade 2 mucositis, or grade 3 AE, except hyperglycemia or hypertriglyceridemia or hypercholesterolemia (see Section 6.2.3.8)	Discontinue Everolimus
Any other grade 4	Discontinue Everolimus
Grade 3 or 4 clinical liver failure (asterixis or encephalopathy/coma)	Discontinue Everolimus

* Should HCV flare be confirmed, the guidelines for flare must take precedence (Table 6-6)

Table 6-2 Dosing guidelines for Everolimus-related hematologic toxicities

Toxicity	Action
Grade 2 thrombocytopenia (platelets $<$ 75, \geq 50 x10 ⁹ /L)	No action
Grade 3 thrombocytopenia (platelets $<$ 50, \geq 25 x10 ⁹ /L)	Discontinue Everolimus
Grade 4 thrombocytopenia (platelets $<$ 25 x10 ⁹ /L)	Discontinue Everolimus
Grade 3 neutropenia or anemia (neutrophil $<$ 1, \geq 0.5 x10 ⁹ /L)	Discontinue Everolimus
Grade 4 neutropenia or anemia	Discontinue Everolimus
Febrile neutropenia	Discontinue Everolimus

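### The protocol gives conflicting everolimus orders for non-infectious pneumonitis: Table 6-1 stops the drug at any grade, while Section 6.2.2.9 and Table 6-3 allow continuation, a half-dose restart or a temporary stop

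*Protocol*

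**What the plan says.** Four places in the protocol tell a site what to do with everolimus when non-infectious pneumonitis occurs.

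- **Section 6.2.1.2, opening rule.** "For patients who do not tolerate the protocol-specified dosing schedule, dose adjustments are not permitted". The section does allow temporary interruption for severe or intolerable reactions.
- **Section 6.2.1.2, Table 6-1.** The row "Non-Infectious Pneumonitis" has the single action of discontinuing everolimus. No grade is given, although the liver enzyme rows of the same table are split by grade.
- **Section 6.2.2.9, text.** At the mild end: "Patients who develop radiological changes suggestive of non-infectious pneumonitis and have few or no symptoms may continue Afinitor therapy without dose alteration". At grade 2, interruption is to be considered, and then "Afinitor may be reintroduced at a daily dose approximately 50% lower than the dose previously administered". At the next grade: "For cases of grade 3 non-infectious pneumonitis, discontinue Afinitor". Grade 4 is also a stop.
- **Section 6.2.2.9, Table 6-3.** Grade 1 needs no dose adjustment. At grade 2, interruption is considered until recovery to grade 1 or lower, and no dose reduction is mentioned. The grade 3 cell reads "Rule out infection and discontinue Everolimus until symptoms improve to Grade", followed by a threshold of 1 or lower. Grade 4 is a stop.

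Section 6.2.2.9 also says: "If non-infectious pneumonitis develops, the guidelines in Table 6-3 should be followed". Section 4.1 supplies the definition that makes the grade 3 cell matter: "dose-limiting toxicity (DLT) is defined as an everolimus-related grade 3 or higher AE".

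**The concern.** An investigator with one patient and one event can find support in the protocol for stopping, for continuing, or for pausing and restarting at half dose, depending on the page consulted. Section 6.2.2.9 itself describes this toxicity as a class effect of rapamycin derivatives that has sometimes been severe and, rarely, fatal. Sites should therefore not have to choose between written orders.

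The grade 3 cell of Table 6-3 is the most awkward. Read alone, it lets a patient resume everolimus after an event that is that patient's own dose-limiting toxicity if it is drug-related. It also disagrees with the text of its own section.

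**Working it through.** The protocol states no figure to reproduce. The check sets the orders side by side, grade by grade. One assumption is needed: the text's category of radiological change with few or no symptoms is taken as grade 1.

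| Grade | Table 6-1 | Section 6.2.2.9 text | Table 6-3 |
|---|---|---|---|
| 1 | Stop | May continue unchanged | No adjustment |
| 2 | Stop | Consider a pause; may restart at about half dose | Consider a pause until grade 1 or lower |
| 3 | Stop | Stop | Stop until grade 1 or lower |
| 4 | Stop | Stop | Stop |

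**Departures from Table 6-1.** Table 6-3 differs at grades 1, 2 and 3, so 3 of 4. The text differs at grades 1 and 2, so 2 of 4. All three sources agree only at grade 4.

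**Departures within Section 6.2.2.9.** Text and table part at grade 2, where only the text has the half dose, and at grade 3, where only the table makes the stop temporary. The half dose and the temporary grade 3 stop therefore come from different sources.

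**Departure from the opening rule of Section 6.2.1.2.** A pause is compatible with that section, which allows interruption. The half-dose restart is not, because it is a dose adjustment.

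**Does the protocol say which source wins?** Section 6.2.2.9 directs sites to Table 6-3 but does not say that it overrides Table 6-1. The only precedence note under Table 6-1 concerns hepatitis C flare. Following Table 6-3 also means disregarding the grade 3 sentence in the section that refers to it.

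**How often could it arise?** Drug is dispensed at Visit 4 (post-RT day 15) for five once-daily doses. If dose 1 is taken that day, the last dose of an uninterrupted course falls on day 15 + 4 = 19, before Visit 5 on day 22. With the one-day visit windows, the tightest case is 16 + 4 = 20 against 21, so the course still ends before the next scheduled visit. Table 7-1 lists no chest imaging, so a purely radiographic grade 1 case would come to light during dosing only by chance. At grade 2, infectious and neoplastic causes have to be excluded first, which leaves few days for a restart. Recovery from grade 3 in time to resume a five-day course is unlikely. The documents give no rate from which an expected number of cases could be computed.

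**The case against.** The strongest reply is that the specific section governs the general table. Section 6.2.2.9 names Table 6-3 as the guide to follow, and Section 6.2.1.2 leaves management to the treating physician's judgment. That reading is available and softens the conflict. It does not settle it, because no precedence over Table 6-1 is stated and because Table 6-3 contradicts its own section at grade 3. It does show that letting Table 6-1 govern is a choice for the sponsor, not something the text already dictates.

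A second reply is that re-treatment after grade 3 is blocked elsewhere. Table 6-1 stops the drug both in the pneumonitis row and in its row for grade 3 events, the Section 6.2.2.9 text says stop, and the glossary defines treatment discontinuation as permanent. This stands: one cell, read alone, is the whole exposure at grade 3.

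A third reply is that a five-day course gives these orders little time to matter. This also stands, at every grade.

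A reader might go further and infer that the half-dose restart is wrong because 2.5 mg is not one of the two dose levels under study. The documents do not support that as an argument against this sentence. Section 4.1 provides for a 50% reduction if mucositis worsens in 2 of the first 6 patients, Section 6.3.1 provides for about 50% with moderate CYP3A4 or PgP inhibitors, and 2.5 mg is a supplied tablet strength. Half doses would remain in the protocol without the pneumonitis sentence. The objection to it is narrower: it contradicts Table 6-1 and the opening rule of Section 6.2.1.2.

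**Conclusion.** The protocol is wrong as written on this point: it contradicts itself on everolimus dosing for non-infectious pneumonitis at grades 1, 2 and 3. The conclusion rests on reading the ungraded row of Table 6-1 as covering every grade, which the graded rows beside it support, and on equating few or no symptoms with grade 1.

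The matter is minor. It is an inconsistency in safety instructions, not a statistical error. A reader might infer that it disturbs the escalation rule or the primary endpoint. The documents do not show that. A dose-limiting toxicity is defined by grade and relation to everolimus, whichever dosing order is then followed, and the saliva sampling times do not change.

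A reader might also extend the point to the grade 2 stomatitis restart in Section 6.2.2.6, on the view that made-up doses could run on late. That would rest on an assumed make-up rule. The schema limits treatment to five days only, and Section 6.1.1 bars an extra dose on the day after a missed one and sends the patient to the study center for advice. The point is therefore confined to pneumonitis.

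**What to change.** Let Table 6-1 govern and bring the other sources into line.

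- **Section 6.2.2.9, text.** Delete the sentence allowing reintroduction at about half dose, and replace the grade 2 instruction with discontinuation.
- **Table 6-3, grade 2 dose cell.** Change to discontinuation, in line with Table 6-1.
- **Table 6-3, grade 3 dose cell.** Change to: *Discontinue everolimus; do not restart.*
- **Grade 1.** Choose one of two options. Either change the Section 6.2.2.9 text and the Table 6-3 cell to discontinuation, or, if the sponsor wants asymptomatic cases to continue, state the exception in Table 6-1: *Grade 1 (asymptomatic, radiographic findings only): continue with monitoring. Grade 2 or higher: discontinue, do not restart.*

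Grade 4 needs no change. The amendment touches wording in Section 6.2.2.9 and Table 6-3, plus Table 6-1 if the grade 1 exception is kept. It adds no visit, test or analysis. The downside is that a rare patient takes fewer than the planned five doses.

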6.2.2.10 Management of hepatitis reactivation / flare

Reactivation of Hepatitis B (HBV) has been observed in patients with cancer receiving chemotherapy (Yeo 2004). Sporadic cases of Hepatitis B reactivation have also been seen in this setting with everolimus. Use of antivirals during anti-cancer therapy has been shown to reduce the risk of Hepatitis B virus reactivation and associated morbidity and mortality (Loomba 2008). A detailed assessment of Hepatitis B/C medical history and risk factors must be done for all patients at screening, with testing performed prior to the first dose of everolimus.

Monitoring and prophylactic treatment for hepatitis B reactivation

Table 6-4 provides detail of monitoring and prophylactic therapy according to the screening results of viral load and serologic markers testing.

Table 6-4 Action to be taken based on screening hepatitis B results

Test	Result	Result	Result	Result	Result
HBV-DNA	+	+ or -	-	-	-
HBsAg	+ or -	+	-	-	-
HBsAb	+ or -	+ or -	+ and no prior HBV vaccination	+ or -	- or + with prior HBV vaccination
HBcAb	+ or -	+ or -	+ or -	+	-
Recommendation	Prophylaxis treatment should be started 1-2 weeks prior to first dose of Everolimus Monitor HBV-DNA approximately every 4-8 weeks		No prophylaxis Monitor HBV-DNA approximately every 3-4 weeks		No specific action

Antiviral prophylaxis therapy should continue for at least 4 weeks after last dose of Everolimus. For HBV reactivation definition and management guidelines, see Table 6-5.

Table 6-5 Guidelines for the management of hepatitis B reactivation

HBV reactivation (with or without clinical signs and symptoms)*

For patients with baseline results: Positive HBV-DNA OR positive HBsAg reactivation is defined as: [Increase of 1 log in HBV-DNA relative to baseline HBV-DNA value OR new appearance of measurable HBV-DNA]	Treat: Start a second antiviral medication AND Discontinue Everolimus administration.
For patients with baseline results: Negative HBV-DNA and HBsAg AND [Positive HBsAb (with no prior history of vaccination against HBV), OR positive HBcAb] Reactivation is defined as: New appearance of measurable HBV-DNA	Treat : Start first antiviral medication AND Discontinue Everolimus

* All reactivations of HBV are to be recorded as grade 3 (e.g. CTCAE Version 3.0 - Investigations/Other: Viral Reactivation), unless considered life threatening by the investigator, in which case they should be recorded as grade 4. Date of viral reactivation is the date on which the rise or reappearance of HBV-DNA was recorded.

Monitoring for hepatitis C flare

The following two categories of patients should be monitored every 4–8 weeks for HCV flare:

- Patients with detectable HCV RNA-PCR test at screening.
- Patients known to have a history of HCV infection, despite a negative viral load test at screening (including those that were treated and are considered ‘cured’)

For definitions of HCV flare and actions to be taken in the event of a flare, please refer to Table 6-6.

Table 6-6 Guidelines for the management of hepatitis C flare

Baseline results	HCV flare definition*	HCV flare management
Detectable HCV-RNA	> 2 log ₁₀ IU/mL increase in HCV-RNA AND ALT elevation > 5 x ULN or 3 x baseline level, whichever is higher.	Discontinue Everolimus
Knowledge of past hepatitis C infection with no detectable HCV-RNA	New appearance of detectable HCV-RNA AND ALT elevation > 5 x ULN or 3 x baseline level, whichever is higher.	Discontinue Everolimus

* All flares of HCV are to be recorded as grade 3 (e.g. CTCAE Version 3.0 - Investigations - Other: Viral Flare), unless considered life threatening by the investigator; in which case they should be recorded as grade 4. Date of viral flare is the date on which both the clinical criteria described above were met. (e.g., for a patient whose HCV-RNA increased by 2 logs on 01 JAN 2011 and whose ALT reached $> 5 \times$ ULN on 22 JAN 2011, the date of viral flare is 22 JAN 2011).

